The data analysis approach for this trial is considered innovative in that it will focus on providing definitive clinical practice guidance through joint evaluation of non-inferiority and quantification of number needed to harm. This parallels how decisions are made in actual clinical practice, as opposed to conventional testing of superiority among respective randomly-assigned treatment regimens. The analytic approach centers on estimation of clinically-relevant parameters that weigh clinical benefit versus harm, thus increasing likelihood of immediate translation of the findings to bedside critical care practice.

In our opinion, this project is highly innovative both in the focus of the intervention and in the methods employed for data collection and analysis.

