The oral care protocol included tooth brushing every 12 hours from the day of admission into the study through day 7. Data were collected on the date of admission to the study and on days 3, 5, and 7. Oral assessments, using 100 mm visual analog scales, were completed in the morning on admission to the study and on days 3, 5, and 7 by a dental hygienist and the bedside nurse. The intervention group mean inflammation scores (mean = 3.9 on scale of 0-10,  $SEM = 3.0$ ) were significantly lower ( $p = 0.0276$ ) than the control group (mean = 12.4 on scale of 0-10,  $SEM = 2.2$ ). Although not statistically significant when analyzed by *t*-test, the experimental group also had lower mean values than the control group on a visual analogue scale of plaque (14.2 vs. 18.3). Despite the measurement by visual analogue scale being less robust than methods in our subsequent studies, this very early study provided us with initial data suggesting that tooth brushing in critically ill patients could affect both mucosal inflammation and dental plaque.

3. Backrest Position and Oral Health: Effect on VAP (R15 NR04730, PI: [name], Co-I: [name]). This non-experimental, longitudinal study of 66 mechanically ventilated adults was conducted to describe 1) the relationship of backrest elevation on the development of VAP, and 2) the relationship of oral health status on the development of VAP. Assessment of oral health status on study days 1, 4, and 7 included biomarker measurement (salivary lactoferrin and IgA), DMFT, a visual analogue scale of dental plaque, and semi-quantitative oral and endotracheal aspirate cultures. Data were analyzed using a mixed linear model.

The analysis of specific aim 2 revealed complex relationships among severity of illness, dental plaque scores at baseline and on day 4, and CPIS at baseline and on day 4. Correlations were significant with day 4 CPIS for APACHE II ( $P=.007$ ), day 4 salivary volume ( $P=.02$ ), interaction of APACHE II score and day 1 CPIS ( $P<.001$ ), and interaction of day 1 CPIS and plaque ( $P=.01$ ). The model indicated that increased dental plaque was most predictive of pneumonia in patients with high APACHE scores and lower baseline CPIS. The number of organisms present in oral cultures increased

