## Key Variables and Measurement

In this final phase of our investigation of oral care in mechanically ventilated adults, our goal is to determine optimal tooth brushing frequency. Taken as a whole, the work conducted in R01 NR007652 (the proposed project combined with the results of the previous and current projects) results in clear, complete, evidence-based guidance for nurses providing oral care to mechanically ventilated adults.

The primary aims of the proposed project are: 1) Evaluate the clinical equivalence (non-inferiority) of three tooth brushing frequencies on oral health (dental plaque and mucosal inflammation) in critically ill adults receiving mechanical ventilation; and 2) Quantify and compare the safety of three tooth brushing frequencies on serious adverse outcomes, including ventilator associated complications and clinically relevant HAIs (including VAP, bacteremia, and sepsis). A secondary aim is to investigate patient factors that influence tooth brushing frequency benefit and risk in critically ill adults.

We will accomplish these objectives using a prospective, randomized, experimental design. Subjects (n=345) will be randomly assigned within 36 hours of intubation to one of three intervention groups which differ in frequency of tooth brushing (once, twice, or three times daily). The intervention, a standardized tooth brushing protocol developed and tested in the previous project, will be delivered by study personnel for 7 days, or until extubated (if extubation occurs within the first 7 days). Key variables and their measurement intervals are presented in Table 1, and will be described more fully in the Research Design section.

Table 1: Key variables

Concept	Variable	Measurement interval
Oral Health (Specific Aim 1)	Dental Plaque: UM-OHI, augmented with DPIA	Daily for 7 days while intubated, days 1,3,5 post-extubation*
	Gingival inflammation: GCF IL-1 $\beta$	Daily for 7 days while intubated, days 1,3,5 post-extubation*
Serious outcomes (Specific Aim 2)	Systemic Inflammatory Response Syndrome criteria	Daily for 7 days while intubated, days 1,3,5 post-extubation*
	HAI: positive epidemiologic surveillance report for VAE (including VAP), bacteremia, sepsis	Daily for 7 days while intubated, days 1,3,5 post-extubation*
	Length of stay (ICU and hospital)	Calculated at hospital discharge
	Length of intubation	Calculated at time of extubation
Patient factors (Specific Aim 3)	Demographics (age, gender, smoking status)	On study admission

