Specific Aim 2 is to quantify and compare the safety of three tooth brushing frequencies on serious adverse outcomes, including ventilator associated complications and clinically relevant healthcare-associated infections. For aim #2, a composite HAI endpoint will be constructed consisting of VAP, bacteremia, and sepsis. Since HAIs are anticipated to be rare events across the 3 tooth brushing regimens, no formal between-group statistical testing will be conducted. Instead, 95% confidence intervals will be calculated for the proportion of subjects with HAI in each treatment arm. In addition, using person days of observation (i.e. days since intubation), we will calculate incidence rates (IR) of HAI by treatment arm and then calculate the number needed to harm (NNH) using the single daily brushing regimen as the

reference group and the formulas:  $NNH_{21} = (1 / (IR_2 - IR_1))$  and  $NNH_{31} = (1 / (IR_3 - IR_1))$  where  $IR_n$  = observed incidence rate in each treatment arm. In the event that the formal test of non-inferiority fails for the single daily brushing regimen, we will define clinically-relevant “compromised” safety as an NNH of 100 per less. This would be interpreted as 100 individuals or less being treated with the multiple daily tooth brushing to develop an HAI that otherwise would not have occurred with the single daily brushing regimen.

Clinical recommendations defined *a priori* and developed from the analyses conducted for aims 1 and 2 will be developed as defined in Table 2.

Table 2. Application of study findings to tooth brushing frequency recommendations

Comparison Groups a	Non-Inferiority	NNH	Recommendation	Rationale
1 versus 3	Supported	N/A	1 time/day	1 time/day non-inferior and safe
1 versus 3	Not supported	$\geq 100$	3 times/day	1 time/day inferior, 3 times/day safe
1 versus 3	Not supported	$< 50$	1 time/day	1 time/day inferior, but 3 times/day safety concern
1 versus 3	Not supported	50 to 100	See 1 vs. 2	1 time/day inferior, but 3 times/day safety concern
1 versus 2 b	Supported	N/A	1 time/day	1 time/day non-inferior and safe
1 versus 2 b	Not supported	$\geq 100$	2 times/day	1 time/day inferior, 2 times/day safe
1 versus 2 b	Not supported	$< 100$	1 times/day	1 time/day inferior, but 2 times/day safety concern

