**Statistical Power and Sample Size Justification.** As described above, our primary aim is to evaluate whether a single daily tooth brushing regimen is clinically non-inferior (defined as an effect size of  $\leq 0.50$ ) to a regimen of brushing twice or 3 times daily. The test is considered one-sided as there is no known or postulated biological mechanism to expect a better clinical result (lower plaque score) with the once daily brushing regimen, while at the same time, no reason to expect a higher risk of serious adverse events with this regimen as compared to 3 times daily brushing. To be conservative, we assume that up to 40% of subjects enrolled will have missing data or not provide analyzable data due to intubation for less than 48 hours or less than 2 days follow-up measurement of dental plaque and mucosal inflammation after intubation; this is consistent with our previous and current projects. The non-inferiority trial is powered based on conventional guidelines of type I error rate ( $\alpha$ ) of 0.10 and 95% desired power, and specifying a 1-tailed tolerance limit for non-inferiority as an effect size of 0.50. With these conditions, a sample size of 69 subjects per group (i.e. testing group 1 versus 3) is required. This group size will also be sufficient if the non-inferiority test is not supported, and a secondary test of the 1 versus 2 times daily brushing regimens is necessary. For 3 groups, the required effective sample size is 207 (69 x 3 groups), which taking into account missing and non-usable outcome data results in a proposed total sample size of 345 subjects (i.e. 207 / 0.60). For specific aim #2, it is difficult to estimate the expected proportion of HAs to occur in the respective treatment arms, particularly given the recent change in Centers for Disease Control and Prevention (CDC) National Healthcare Safety Network (NHSN) surveillance definitions for ventilator associated complications, including VAP. If the proportion of subjects who experience HAI within one of the treatment groups ( $n=69$ ) is 0.05, the corresponding 95% confidence interval would be 0.01 to 0.13, indicating reasonable precision.

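### Table 2 labels once-daily brushing safe on the plaque result, without the infection comparison for that row, and has no row for excess infections in the once-daily arm

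*Combined protocol and SAP*

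**What the plan says.** Safety is the second of two primary aims (Key Variables and Measurement): "Quantify and compare the safety of three tooth brushing frequencies on serious adverse outcomes, including ventilator associated complications and clinically relevant HAIs". The Innovation section describes the analysis as "joint evaluation of non-inferiority and quantification of number needed to harm", and the Summary in section VII repeats the idea. The Aim 2 text in section XI says that the clinical recommendations are "developed from the analyses conducted for aims 1 and 2 will be developed as defined in Table 2".

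Table 2 has two rows in which non-inferiority is supported, one for 1 versus 3 and one for 1 versus 2. Both give NNH as N/A, recommend once daily, and state "1 time/day non-inferior and safe".

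The Aim 2 text defines NNH31 = 1/(IR3 − IR1) and NNH21 = 1/(IR2 − IR1), with IR an incidence rate from person-days. Its threshold for compromised safety, an NNH of 100 or less, applies "In the event that the formal test of non-inferiority fails for the single daily brushing regimen". The descriptive output carries no such condition: "95% confidence intervals will be calculated for the proportion of subjects with HAI in each treatment arm", followed by incidence rates and NNH. No formal between-arm test of HAI is planned.

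Footnote b to Table 2 opens the 1 versus 2 rows only if 1 versus 3 is not supported and NNH31 is between 50 and 100. The Aim 1 text requires only that 1 versus 3 is not supported.

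The Statistical Power and Sample Size Justification says of once-daily brushing that there is "no reason to expect a higher risk of serious adverse events with this regimen as compared to 3 times daily brushing".

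**The concern.** A safety conclusion should come from safety data. In the 1 versus 3 Supported row it comes from a plaque test, backed only by the premise in the power section. Supported excludes a plaque disadvantage of 0.50 SD or more; it does not exclude a smaller one. The sponsor's own earlier work gives some reason to check whether more plaque carries infection risk. Of the backrest study (Preliminary Studies, study 3) the protocol says: "The model indicated that increased dental plaque was most predictive of pneumonia in patients with high APACHE scores and lower baseline CPIS".

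Table 2 also looks for harm in one direction only, from more brushing. If the once-daily arm had more VAP, bacteremia or sepsis, the table has no place to say so. The plan intends this table to yield practice recommendations, so the word safe would travel with the result.

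**Working it through.** **1. The plan's figures reproduce.** Inputs (Statistical Power section): margin 0.50 SD, one-sided alpha 0.10, power 95%, true difference 0. The result is 69 per group; 69 × 3 = 207; 207/0.60 = 345, or 115 enrolled per arm. For an HAI proportion of 0.05 with n = 69, the exact (Clopper-Pearson) 95% interval is 0.012 to 0.131, matching the stated 0.01 to 0.13.

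**2. How often the 1 versus 3 Supported row is reached if plaque is truly equal.** The standard error of the standardised difference is √(2/69) = 0.170, and 0.50/0.170 = 2.937.
- Two-sided 95% interval, as in the Aim 1 text: Φ(2.937 − 1.960) = 0.836.
- One-sided alpha 0.10, as in the power section: Φ(2.937 − 1.282) = 0.951.

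This is the most likely path under the design assumption. The row reads the same whatever the HAI rates are.

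**3. Which infection result enters each Supported row.**
- 1 versus 3: none.
- 1 versus 2 under footnote b: NNH31 must already lie between 50 and 100. That is positive, so IR3 exceeds IR1 and once daily has shown fewer HAI than three times daily. NNH21 is not used.
- 1 versus 2 under the Aim 1 text: none.

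**4. Negative NNH.** Suppose, for illustration only, IR1 = 0.10 and IR3 = 0.05 in the same unit. Then NNH31 = 1/(0.05 − 0.10) = −20. Read literally, −20 is below 50, so the not-supported 1 versus 3 row recommends once daily and gives a safety concern with three times daily, the reverse of what was observed. A negative NNH21 falls in the below-100 row with the same effect.

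**5. What the HAI data could show.** With 5% HAI in each arm, the 95% half-width for the difference is 1.96 × √(2 × 0.05 × 0.95/n):
- n = 115: 0.056
- n = 69: 0.073

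Under assumed risks of 10% once daily and 5% three times daily (the documents give no arm-specific rates), the once-daily arm has more HAI cases in 91% of trials at 115 per arm, counting any excess, even one case. Two-sided 5% power for that contrast is 0.30 at 115 per arm and 0.20 at 69.

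**6. A 1-per-100 point-estimate trigger.** With equal 5% risk in both arms, exact binomials give an observed once-daily excess of at least 1 point in 32% of trials at 115 per arm and 42% at 69.

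**The case against.** The best defence is that Aim 2 is to quantify and compare, and the plan does so whatever the plaque result: HAI proportions with intervals, incidence rates and NNH are reported by arm. That stands. A reader might infer from Table 2 that a primary aim is declared met without its data being consulted. The documents do not say that; an HAI excess with once-daily brushing would still appear in the results. What bypasses it is the rationale and the recommendation.

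A reader might also infer that no infection result enters either Supported row. Under footnote b that is wrong for 1 versus 2, because NNH31 has already been used.

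A third tempting reading is that the backrest study contradicts the power section's premise. It does not do so directly. It was a non-experimental study of 66 adults, the association was strongest in a subgroup, and it concerns plaque level rather than brushing frequency. The sponsor's randomised trial points the other way: brushing three times daily lowered plaque, had no effect on the pulmonary infection score (p = .54), and showed a non-significant trend to worse (Background and Significance; Preliminary Studies, study 1). Looking mainly for harm from more brushing was therefore a reasoned choice. Mixed evidence is still a reason to read the trial's own HAI result before using the word safe.

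Finally, the 10% versus 5% scenario is assumed and runs against that randomised trend. It illustrates the rule and is not a forecast.

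**Conclusion.** The point holds as a fault in the decision table. In the 1 versus 3 Supported row the label safe follows from plaque alone, and in the 1 versus 2 Supported row it is given without NNH21. An HAI excess in the once-daily arm has no row, and a literal reading of a negative NNH reports it as a concern about more frequent brushing. This conflicts with the promised joint evaluation and with safety being a primary aim.

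The 1 versus 3 Supported row is reached with probability 0.84 to 0.95, assuming exactly equal plaque and 69 analysable subjects per arm. The documents do not show that once-daily brushing is unsafe, and this point does not claim it. Nor could the trial's HAI data establish safety by themselves, with an interval of about ±5.6 to ±7.3 points at an assumed 5% per arm. The wording should be corrected before analysis.

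**What to change.** - In every row of Table 2, report the signed HAI difference (once daily minus comparator) with its 95% interval, and state whether it is on the subject-proportion or the person-day scale.
- Replace the rationale in both Supported rows with non-inferior on plaque, and take any safety statement from that interval.
- State how a negative NNH is read, so that it cannot fall into the rows for a concern about more frequent brushing.
- Reconcile the Aim 1 text with footnote b on when the 1 versus 2 comparison is made.
- Keep the power section's statement, but present it as an assumption to be checked against the trial's HAI data, citing both the backrest study and the randomised trial.
- Do not add a rule that flags a concern at an observed excess of 1 per 100. It would fire by chance in about 32% to 42% of trials with equal 5% risk, and it would mix subject proportions with the plan's person-day rates.

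The cost is revised wording in Table 2 and the text, plus a difference and interval derived from arm-level HAI results already planned. Design, endpoints and sample size do not change. The downside is that the safety statement will often be inconclusive and the recommendation less clear-cut.

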## Justification and Feasibility

Dental plaque is a significant factor in oral health, with implications for systemic health. Dental plaque is a complex biofilm found on tooth surfaces, and plaque accumulation is enhanced by bacterial aggregation between and among species. Microbial flora are concentrated in dental plaque, which is a complex environmental niche of interdependent microorganisms embedded in bacterial and salivary products.

Accumulation of dental plaque is closely associated with oral inflammation, including gingivitis and periodontitis. The standard clinical experimental model for gingivitis involves holding of tooth brushing to induce or exacerbate the disease. In healthy adult subjects who withheld tooth brushing, Scott and colleagues found a progressive, positively correlated increase in dental plaque and GCF biomarkers over the 21 day study period; when inflammation was assessed again after 7 days of brushing resumption, it had resolved. Further, they found that GCF IL-1 $\beta$  increased after 3 days of plaque accumulation, in advance of clinical signs of inflammation. When measured over shorter intervals in a briefer study (tooth brushing withheld for 3 days), Zhang and colleagues found that GCF IL-1 $\beta$  elevated after one day, and returned to baseline within 2 days of resumption of brushing.

Oral mucosal inflammation, and in particular gingivitis or periodontal disease, provides opportunities for bacterial overgrowth, and richly vascularized and inflamed tissues associated with these diseases are susceptible to bacterial invasion. Gingivitis and periodontitis are known to increase the risk of bacteremia related to invasive dental procedures in healthy populations. Paradoxically, tooth brushing has also been linked to transient bacteremia in healthy subjects. In critically ill adults, central line catheters are the predominant but not the sole source for bacteremia. The role of other sources, including tooth brushing, has not been elucidated.

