While the plaque assessment procedures used in our previous project worked sufficiently, we believe that documenting the condition of the teeth using an intraoral camera, in conjunction with plaque assessors applying UM-OHI assessment to those images, will provide several important advantages. Digital images of subjects' teeth provide documented, archival raw data which can be scored by multiple plaque assessors as needed to enhance both reliability and inter-rater reliability. Positioning the camera in the oral cavity will provide better visualization of the lingual surfaces of teeth, particularly teeth in proximity of the endotracheal tube, than direct external observation; this will enhance detection of plaque on surfaces which are difficult to directly observe. Intraoral imaging can be done more quickly than full bedside assessment, reducing any subject discomfort during the assessment. Conducting the UM-OHI scoring in the research office rather than at the bedside enhances blinding of the assessment. These procedures will also make the most efficient use of plaque assessor expertise.

**Oral Health: Oral Mucosal Inflammation.** We will quantify mucosal inflammation by determination of GCF IL-1 $\beta$ . Collection GCF is a well-developed dental research methodology dating to the 1960s, and has elements common to our expertise in collection of saliva and quantification of salivary biomarkers. GCF samples will be obtained prior to the first tooth brushing intervention, and daily every day for the first seven days of intubation. If extubated during the 7 day intervention period of the study, GCF samples will also be obtained on days 1,3 and 5 post-extubation to document resolution or persistence of inflammation after resumption of self-administered oral hygiene. Periopaper strips will be placed into the gingival margins of the maxillary premolars for thirty seconds; if these teeth are not present, the next adjacent teeth will be used. Using published methods, samples will be placed in PBS-BSA transport medium and frozen at -70°C until assay, when the GCF analytes will be eluted from the paper strips and assayed in duplicate for IL-1 $\beta$  using a commercial enzyme-linked immunosorbent assay (ELISA) system according to the manufacturer's instructions.

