aTimes per day of tooth brushing. bConducted if the 1 versus 3 test of non-inferiority is not supported and  $NNH_{31}$  is between 50 to 100. NNH: number needed to harm.

Specific Aim 3, to investigate patient factors that influence tooth brushing frequency benefit and risk in critically ill adults, is considered exploratory. Repeated measures linear mixed models will be fit treating dental plaque and mucosal inflammation as separate outcome variables (transformed if required), random group assignment as a 3-level ordinal predictor variable, and a range of possible patient-level predictors. Initially, bivariate correlations for potential continuous predictors and analysis of variance (ANOVA) for potential categorical predictors will be conducted to identify potential patient factors independently associated with dental plaque and mucosal inflammation. Interaction terms between tooth brushing frequency (scored 1, 2, or 3) and individual patient factors will be constructed to assess potential effect modification. The mixed models will be fit using the normal distribution, identity link, and specifying an autoregressive correlation structure. For assessment of safety, and assuming a sufficient number of HAs for model conversion, generalized estimating equations will be fit in the same manner as the linear mixed models while specifying the binomial distribution, log link, and an autoregressive correlation structure. Through these analyses, we aim to gain insight as to specific patient factors (e.g. presenting oral health) that may modify the clinical effectiveness and safety profile associated with frequency of tooth brushing.

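### The Aim 3 mixed models, the only between-group analysis of GCF IL-1β, name no baseline covariate or study-day term and do not say which samples are responses

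*Combined protocol and SAP*

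**What the plan says.** Section XI (Data Analysis Plan), under Specific Aim 3, specifies the models: "Repeated measures linear mixed models will be fit treating dental plaque and mucosal inflammation as separate outcome variables". The predictors are "random group assignment as a 3-level ordinal predictor variable, and a range of possible patient-level predictors". Effect modification is covered by this sentence: "Interaction terms between tooth brushing frequency (scored 1, 2, or 3) and individual patient factors will be constructed to assess potential effect modification". Time appears only in the correlation, by "specifying an autoregressive correlation structure". The aim is called exploratory.

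The samples come from Key Variables and Measurement. For IL-1β, "GCF samples will be obtained prior to the first tooth brushing intervention", then daily for up to seven days of intubation. For subjects extubated in that period, "GCF samples will also be obtained on days 1,3 and 5 post-extubation". Plaque (UM-OHI) follows the same schedule. The footnote to Table 1 says that subjects still intubated beyond seven days have no post-extubation data.

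Under Specific Aim 1, section XI compares plaque between groups by ANCOVA, with baseline plaque and timing of assessment as covariates. Mucosal inflammation is named in that aim, but no test is given for it.

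**The concern.** Each subject's record can hold three kinds of sample. The pre-brushing sample cannot carry an effect of assigned frequency. The on-regimen samples can. The post-extubation samples are taken once the assigned schedule has ended and self-care has resumed. Justification and Feasibility reports that IL-1β in healthy adults rose after one day without brushing and "returned to baseline within 2 days of resumption of brushing", so loss of the effect by post-extubation days 3 and 5 is plausible for that marker. It is not shown for ventilated patients, and nothing comparable is cited for plaque.

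A single frequency coefficient fitted to all three kinds averages an effect with samples that hold none, or only part, of it. An autoregressive correlation does not correct this, because it describes residuals and not means. A main effect of day would not correct it either: it shifts all groups alike and still forces one frequency effect across all phases.

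What is at stake is the trial's only between-group reading of IL-1β and its search for moderators. Because the text leaves the responses and the baseline adjustment open, both could be chosen after the data are seen.

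**Working it through.** **1. The plan's own figure.** Inputs from the sample size paragraph of section XI: one-sided α 0.10, power 95%, margin 0.50 SD; true difference 0 is taken. n = 2 × [(1.2816 + 1.6449) / 0.50]² = 68.5, so 69 per group; 3 × 69 = 207; 207 / 0.60 = 345. This reproduces the plan. The figure belongs to the Aim 1 plaque test; none is stated for the mixed models.

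**2. The two analyses side by side.**

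| | Aim 1 ANCOVA (plaque) | Aim 3 mixed models (plaque, IL-1β) |
|---|---|---|
| Baseline response | covariate | not named |
| Time | covariate | correlation only |
| Which samples | largest change since baseline | not stated |

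**3. Dilution if all samples were pooled.** The schedule gives one pre-brushing sample (placed at day 0), samples on brushing days 1 to k and, for k below 7, samples at days k+1, k+3 and k+5. The following are assumptions, not in the documents: daily autocorrelation ρ of 0.3 to 0.7 on actual days; a constant effect on all brushing days; and either none (c = 0) or all (c = 1) of the effect remaining after extubation. The mean model has an intercept and group only.

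The expected coefficient, as a share of the on-regimen effect, is Σwd / Σw. Here d is 0 at baseline, 1 on brushing days and c after extubation, and w are the generalised least squares weights. With a = 1/(1+ρ) and b = 1/(1+ρ²), the weights are: pre-brushing a; each brushing day 2a−1; post-extubation day 1 a+b−1; day 3 2b−1; day 5 b. Adding a random intercept leaves the shares unchanged.

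*k = 7, no post-extubation samples.* Share = 1 − 1/[2 + 6(1−ρ)]:
- ρ = 0.3: 1 − 1/6.2 = 0.84
- ρ = 0.5: 1 − 1/5.0 = 0.80
- ρ = 0.7: 1 − 1/3.8 = 0.74

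*k below 7.* With D = k(2a−1) + 2a + 4b − 2, the share is k(2a−1)/D for c = 0 and 1 − a/D for c = 1. At ρ = 0.5, a = 0.6667 and b = 0.8. For k = 4, D = 1.3333 + 2.5333 = 3.8667, giving 1.3333/3.8667 = 0.34 and 1 − 0.6667/3.8667 = 0.83.

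| Brushing days k | c = 0, ρ = 0.3 / 0.5 / 0.7 | c = 1, ρ = 0.3 / 0.5 / 0.7 |
|---|---|---|
| 2 | 0.25 / 0.21 / 0.16 | 0.82 / 0.79 / 0.73 |
| 4 | 0.40 / 0.34 / 0.27 | 0.86 / 0.83 / 0.77 |
| 6 | 0.50 / 0.44 / 0.36 | 0.88 / 0.85 / 0.80 |

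An intermediate case keeps the effect on post-extubation day 1 only. At k = 4 and ρ = 0.5 it gives (1.3333 + 0.4667)/3.8667 = 0.47. With responses limited to brushing days the share is 1.00.

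**4. Interactions.** At ρ = 0.5 and c = 0, the same true effect shows as 0.21 in a subject brushed for 2 days and 0.80 in one brushed for 7. If a factor such as APACHE is related to length of intubation (an assumption), the mix of samples alone could create a frequency-by-factor interaction, or mask a real one of opposite sign.

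**5. Precision from the baseline covariate.** Under pure AR(1), with brushing-day responses only, precision is proportional to [2 + (k−2)(1−ρ)]/(1+ρ) unadjusted and [(k−1)(1−ρ)² + 1]/(1−ρ²) adjusted.
- k = 7, ρ = 0.3: 4.231 against 4.330. The standard error falls by 1 − √(4.231/4.330), about 1%.
- k = 2, ρ = 0.7: 1.176 against 2.137. It falls by about 26%.

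If half the variance is a stable subject effect, the gain is larger. With SD 1 and 69 per group, the standard error falls from 0.155 to 0.116 (25%) at k = 2, ρ = 0.3, and from 0.164 to 0.088 (46%) at k = 2, ρ = 0.7.

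**The case against.** The strongest reply is that this is an under-specified model, not a biased one. A reader might infer that the plan pools every sample into one series and so roughly halves the effect. The documents do not support that: section XI neither includes nor excludes any visit. Some text points towards separation. Key Variables and Measurement gives the post-extubation samples their own purpose (whether plaque or inflammation resolves or persists), and the Summary in section VII describes the measures as daily during the intervention period before it introduces the mixed models. Dilution is therefore conditional, and a simple count of samples does not give its size, because the planned correlation does not weight samples equally.

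Three further inferences would also go too far:

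- That baseline values are ruled out. The predictor list is open and the stated interest is in "specific patient factors (e.g. presenting oral health", which could admit baseline plaque or IL-1β. The list is also wider than the Aim 3 rows of Table 1, since section XVI commits to race and ethnicity. However, the only measure tied by name to pre-existing oral health is DMFT, a count of decayed, missing and filled teeth.
- That the autoregressive structure treats two-day gaps as one-day gaps. The text does not say whether it is indexed by visit or by day.
- That every interaction shrinks towards zero. Step 4 shows that the error can go either way.

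The models are also exploratory, and baseline plaque is already adjusted for in the primary test. All of this limits the reach of the point. The gap itself remains: the plan names baseline and timing for plaque in Aim 1 and neither for its only IL-1β comparison.

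**Conclusion.** The point stands as a free improvement. The Aim 3 mean model names no baseline response and no study day, and the choice of response samples is left open. If all samples were pooled, about 74-84% of the on-regimen effect would be recovered for a subject with 7 brushing days and no post-extubation samples. For subjects extubated after 2 to 6 brushing days, the range is 16-50% with no residual effect and 73-88% with full retention. These figures rest on assumed autocorrelation, carry-over and a constant on-regimen effect, and they describe single patterns of sampling; the trial's coefficient would be a mixture of them. The pre-brushing sample dilutes under every assumption tried; the post-extubation contribution depends on carry-over that the documents do not establish in this population. Only the exploratory Aim 3 results are affected. The non-inferiority test, the Table 2 recommendation and the sample size of 345 are not.

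**What to change.** In section XI, Specific Aim 3, state that:

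- the responses are samples taken after the first study brushing and while the subject is intubated;
- the subject's own pre-brushing value (UM-OHI, or IL-1β transformed as needed) is a covariate;
- study day is in the mean model;
- pre-brushing value by frequency is named among the exploratory moderators;
- post-extubation samples are analysed in a separate model, or with a phase term and its interaction with frequency;
- the correlation is based on actual days.

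Keeping the pre-brushing value in the response with equal group means at baseline would be an acceptable alternative to the covariate.

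The cost is a few sentences of plan text before the data are examined. Every value needed is already scheduled, and no visit, assay or subject is added.
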